## COHORT 1 SUBSTUDY TIME AND EVENTS SCHEDULE

### Subjects at Selected Sites Receiving a Third Vaccination (Cohort 1, Groups 1-2)

Groups 1 & 2 b	Vaccination Phase and Post-vaccination Phase					Long-term Follow-up Phase a	
	1 Year Post Prime + 3 months	D2-D7 Post 3 rd Vaccination	D5 Post 3 rd Vaccination	D8 Post 3 rd Vaccination	D22 Post 3 rd Vaccination	D180 Post 3 rd Vaccination	D365 Post 3 rd Vaccination
Study procedures	3rd Vaccination		+4d p3v	+7d p3v	+21d p3v	+6m p3v	+1y p3v
Screening/Administrative							
Informed consent c	X						
Study vaccine administration	▲ d						
Safety assessments							
Urine pregnancy test e	X f						
Physical examination g	X f		X	X	X	X h	X h
Vital signs i	X f						
Distribution of subject diary	X						
Completion of diary at home j		X					
Review of diary by site staff				X			
Adverse events k	Continuous until 28 days after the third vaccination a,l						
Serious adverse events and immediate reportable events m	Continuous a,l						
Concomitant medications	X		X	X	X	X n	X n
Clinical Laboratory Assessments							
Chemistry, hematology (10 mL) o	X f			X			
Immunogenicity Assessments p							
Blood sampling (serum) for assessment of humoral immune responses (10 mL)	X f		X	X	X	X	X
Blood sampling (PBMC) for assessment of cellular immune responses (40 mL) q	X f				X		X
Approximate Blood Volumes with [without] PBMC r							
- By visit (mL) r Cohort 1 (Group 1 and 2)	60 [20]		10	20	50 [10]	10	50 [10]
- Cumulative (mL) r Cohort 1 (Group 1 and 2)	60 [20]		70 [30]	90 [50]	140 [60]	150 [70]	200 [80]

▲ Ad26.ZEBOV 5x10^7 vp or placebo

d p3v: days post third vaccination; m p3v: months post third vaccination; y p3v: year post third vaccination

**NOTE:** In case of early withdrawal from the study, early withdrawal assessments (ie, physical examination and immunogenicity assessments for serum) should be obtained. Subjects who wish to withdraw consent will be offered an optional visit for safety follow-up (before the formal withdrawal of consent); the subject has the right to refuse.

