### **3.2. Study Design Rationale**

The study design is largely driven by the accelerated development approach of the Ad26.ZEBOV and MVA-BN-Filo prime-boost combination. Based on the growing availability of data from the entire development program as the study proceeds, modifications to the study design may be considered. For instance, if the results from the 28-day prime-boost interval (or any other interval) are not favorable based on the evaluation of the NHP and Phase 1 data (safety and immunogenicity) as soon as these become available, the enrollment in this group will be stopped (if not yet completed). When enrollment in one of the regimens will be stopped, the number of subjects still to be enrolled for this regimen will be randomized to the other regimen(s) to ensure that the same number of subjects can be included in an overall safety database of the Ad26.ZEBOV and MVA-BN-Filo prime-boost regimen.

The interruption in dosing and subsequent restart has required changes to the management of the subjects affected by the pause. All subjects (including placebo) who were primed prior to the pause and did not/will not receive a late boost vaccination will be followed for safety. Subjects

who did/will receive a late boost vaccination will follow the same post-boost vaccination schedule as those subjects unaffected by the pause (for details, see Section 9.1.6).

Immunogenicity data from a Phase 1 study (VAC52150EBL1002) demonstrated stability of the binding antibody response out to 1 year following prime-boost regimens with Ad26.ZEBOV/MVA-BN-Filo (or the reverse). A third vaccination using Ad26.ZEBOV at  $5 \times 10^{10}$  vp was given at the 1-year time point leading to a marked and rapid increase in the binding antibody responses within 7 days (at least 10-fold). The marked and rapid rise was generally independent of the antecedent prime-boost regimen. The profile of the antibody strongly suggests that robust anamnestic responses can be induced after re-exposure to an EBOV antigen, in this case mimicked by a third vaccination. Administration of a third vaccination with Ad26.ZEBOV at least 1 year post prime for approximately 90 subjects in Cohort 1 will extend the findings to an African population and confirm the immunogenicity profile from the Phase 1 study.

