2. GENERAL ANALYSIS DEFINITIONS

The type I error rate (α) is set to 0.05 and corresponding 2-sided 95% confidence intervals (CIs) will be calculated wherever applicable. Adjustment of the α (type I error) level due to multiplicity is not applicable for this study as no planned formal statistical hypothesis testing will be performed.

The analysis is defined separately for each parameter later in this document together with the description of rules for handling missing or incomplete data. The analysis will include vaccinated subjects with respect to the actual vaccine administered. The subjects who received only Ad26.ZEBOV prime vaccination will be included in accordance with the group to which they were randomization. On the other hand, any subject who was vaccinated according to MVA-BN-Filo prime only, MVA-BN-Filo prime/Ad26.ZEBOV boost or a homologous schedule (ie, Ad26.ZEBOV prime/Ad26.ZEBOV boost or MVA-BN-Filo prime/MVA-BN-Filo boost) will be excluded from summary tables and graphs, and listed separately.

In general, the study data will be analyzed as follows:

- Categorical variables will be summarized with a frequency table presenting counts and percentages.
- Continuous variables will be summarized using the following statistics, as appropriate: number of observations, arithmetic mean, geometric mean, corresponding 95% CI, standard deviation, standard error, median, quartiles (Q1 and Q3), minimum and maximum.

Baseline value will be defined as the value of the last available assessment performed prior to the prime vaccination, unless specified otherwise.

For safety assessments, the *baseline value* will be an assessment performed prior or on the date (if only time of assessment is missing) of the prime vaccination. The baseline value for immunogenicity assessments will be an assessment performed before or on the date of the prime vaccination. In case of multiple values, the value closest to the vaccination will be used as the baseline.

Reference value (only for immunogenicity) will be defined as the assessment performed on the date of the boost vaccination. In case of multiple values (on the same day of vaccination), the value closest to the vaccination will be used as the reference value.

Visit day will be determined relative to the actual day of vaccination (ie, date of Doses 1, 2 or 3).

Repeated assessments of immunogenicity and safety will be allocated to analysis windows and periods based on

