6.2. Immunogenicity Against the Insert

6.2.1. Humoral Immune Responses

6.2.1.1. Parameters

Humoral immune responses, as measured by the following assays, will be analyzed:

- **Binding antibody responses using Filovirus Animal Nonclinical Group (FANG) ELISA:** Quantification of antibodies binding to EBOV GP using the ELISA units/mL readout.

In addition, the following will be defined for ELISA (units/mL) binding antibody responses:

- **Sample interpretation:** A sample will be considered positive, if the value is above the lower limit of quantification (LLOQ).
- **Responder:**
 - If sample interpretation is negative at baseline but positive post-baseline and the post-baseline value is greater than 2.5×LLOQ; OR
 - If sample interpretation is positive at both baseline and post-baseline and there is a greater than 2.5-fold increase from baseline (2.5-fold increase on the original scale).
- **Neutralizing antibody responses using VNA:** titers of EBOV GP-specific neutralizing antibodies (unit: 50% inhibitory concentration [IC₅₀]).

For VNA (IC₅₀) responses, the following will also be defined:

- **Sample interpretation:** a sample is considered positive if the value is greater than both the assay-specific LLOQ and $3 \times$ (amphotropic murine leukemia virus [aMLV]). Otherwise, the sample is considered negative.
- **Responder:**
 - If sample interpretation is negative at baseline but positive post-baseline and the post-baseline value is greater than $2 \times$ LLOQ; OR
 - If sample interpretation is positive at both baseline and post-baseline and there is a greater than 2-fold increase from baseline (2-fold increase on the original scale).

Important: The pseudovirions used in the pseudo VNA (psVNA) are constructed using an HIV-genomic luciferase vector. During assay validation, a high non-EBOV GP-specific background signal was observed for 1 out of 3 HIV-positive sera tested. Hence, the accuracy of the quantitative measurement of the neutralizing antibody response can be affected in HIV+ serum samples. Therefore, the above responder definition will not be used for the HIV-infected cohort and only a qualitative readout of the psVNA will be reported for the HIV-infected cohort, using the VNA sample interpretation to classify a sample as either negative or positive.

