6.2.1.3. Analysis Methods

The humoral immune responses (ELISA [units/mL] and VNA [IC_{50} titer]) will be evaluated separately for each cohort. Within each cohort, the data will be presented by vaccination schedule. See Section 2.4 (and Table 4) for details on the subgroup analyses that will be performed.

Except for VNA analysis of the HIV-infected subjects (Cohort 2a), the humoral immune responses of all other cohorts will be analyzed as follows. Summary statistics (ie, geometric means and corresponding 95% CIs) will be calculated and presented for ELISA (units/mL) binding antibody responses and VNA (IC_{50} titers) at each time point. The geometric mean fold increase (from Pre-dose 1, Pre-dose 2 and Pre-dose 3 [only for the Cohort 1 substudy]) with corresponding 95% CI will also be presented per time point for these parameters.

Regimen profiles of the geometric mean concentrations with 95% CIs will be presented. Additional regimen profiles of the geometric mean concentrations with 95% CIs will be generated by pre-existing antibody response against Ad26 vector (ie, pre-existing Ad26 versus no pre-existing Ad26). In addition, graphs of the reverse cumulative distributions (ie, percentage of subjects versus the magnitude of the antibody response levels) will be provided for the following time points, if available:

- Baseline and Pre-dose 2
- Baseline and Day 21 Post-dose 2
- Baseline and 180 days Post-dose 2
- Baseline and Day 365 Post-dose 1
- Baseline and 4 days Post-dose 3
- Baseline and 7 days Post-dose 3
- Baseline and 21 days Post-dose 3
- Baseline and Day 180 Post-dose 3
- Baseline and Day 365 Post-dose 3

For both ELISA (ELISA units/mL) and VNA (IC₅₀ titer), additional graphical representations (on a log₁₀-scale) will be provided using dot plots (with distinction between positive and negative sample interpretations), by vaccination schedule.

Responder rates and positive sample interpretation will be summarized (ie, showing number, percentage and the exact 95% Clopper-Pearson CI) for ELISA (ELISA units/mL) antibody responses and VNA (IC₅₀ titers) per time point. A data listing will also be generated.

For the HIV-infected subjects (Cohort 2a), only positive sample interpretation will be summarized (ie, showing number, percentage and the exact 95% Clopper-Pearson CI) per time point.

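### After the third vaccination the responder rate is measured against the pre-prime sample, so it mixes persistence of the prime-boost response with response to dose 3

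*SAP*

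**What the plan says.** SAP section 2 gives a general rule, "Baseline value will be defined as the value of the last available assessment performed prior to the prime vaccination, unless specified otherwise", and a specific one for this data type: "The baseline value for immunogenicity assessments will be an assessment performed before or on the date of the prime vaccination". The only other comparator defined there is tied to dose 2: "Reference value (only for immunogenicity) will be defined as the assessment performed on the date of the boost vaccination".

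SAP 6.2.1.1 has two routes to ELISA responder status. For a subject negative at baseline: "If sample interpretation is negative at baseline but positive post-baseline and the post-baseline value is greater than 2.5×LLOQ". For a subject positive at baseline: "If sample interpretation is positive at both baseline and post-baseline and there is a greater than 2.5-fold increase from baseline". The VNA rule in the same section, and the ELISpot and ICS rules in 6.2.2.1, follow the same pattern with a multiple of 2. None has a separate clause for dose 3.

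On reporting, SAP 6.2.1.3 states "Responder rates and positive sample interpretation will be summarized", per time point and with exact intervals. SAP Table 1 has five visits after dose 3 (4, 7, 21, 180 and 365 days) and a separate Pre-dose 3 visit. For humoral responses, 6.2.1.3 also plans geometric mean fold increases from Pre-dose 1, Pre-dose 2 and, in the substudy, Pre-dose 3.

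**The concern.** By the time of dose 3, an active substudy subject has had two vaccinations since the sample that serves as baseline. Protocol 3.2 reports that the Phase 1 data "demonstrated stability of the binding antibody response out to 1 year following prime-boost regimens", followed by at least a 10-fold increase within 7 days of a third dose. If antibody persists in this population too, many active subjects may already satisfy the responder rule just before dose 3. They would go on satisfying it a few days later whether or not dose 3 did anything.

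The third-vaccination design rationale in Protocol 3.2 concerns the anamnestic response. A post-dose 3 responder rate will naturally be read as the share of subjects who responded to dose 3, and under the present definition it is not that. The same weakness affects the planned comparison in SAP 2.3 of subjects given dose 3 within 30 days after Day 365 with those given it later: a rate carried largely by persistence would separate the two groups poorly.

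**Working it through.** The documents state no responder rate or power for this point, so there is no figure to reproduce. The check applies the rule as written.

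**Inputs**
- Comparator: pre-prime sample (SAP section 2).
- ELISA rule: above 2.5×LLOQ if baseline is negative, more than 2.5-fold over baseline if positive (SAP 6.2.1.1).
- SD of log10 ELISA: 0.3, 0.4, 0.5 (Protocol Table 10).
- R, the pre-dose 3 geometric mean divided by the LLOQ: not in the documents. Assumed, from 1 to 50.
- Substudy size: about 90. If the 5:1 ratio carries over to volunteers at selected sites (an assumption), 90 × 5/6 = 75 active and 90/6 = 15 placebo.

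**Step 1: individual cases for ELISA, in multiples of LLOQ**

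| Pre-prime | Pre-dose 3 | Post-dose 3 | Responder as written | Responder vs Pre-dose 3 |
|---|---|---|---|---|
| <1 | 20 | 20 | yes | no |
| <1 | 20 | 10 | yes | no |
| 4 | 12 | 12 | yes (3-fold) | no |
| <1 | 2 | 2 | no | no |
| <1 | 4 | 2.4 | no | no |
| 4 | 8 | 8 | no (2-fold) | no |
| <1 | <1 | <1 | no | no |
| <1 | 20 | 200 | yes | yes |

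The first three subjects do not rise, and in the second the value halves, yet all three count. The next four also do not rise and do not count. The true 10-fold riser counts under either comparator.

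**Step 2: how often a baseline-negative non-riser is counted at one visit**

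With log10 values normal and unchanged by dose 3, P = 1 − Φ((log10 2.5 − log10 R)/SD). For example, R = 5 and SD = 0.4 gives (0.398 − 0.699)/0.4 = −0.753, so P = 77%.

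| R | SD 0.3 | SD 0.4 | SD 0.5 |
|---|---|---|---|
| 1 | 9% | 16% | 21% |
| 2 | 37% | 40% | 42% |
| 5 | 84% | 77% | 73% |
| 10 | 98% | 93% | 89% |
| 20 | 99.9% | 99% | 97% |
| 50 | 100% | 99.9% | 99.5% |

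Putting the VNA multiple of 2 in place of 2.5, with the same SDs, gives 16 to 27% at R = 1 and 92 to 99% at R = 10. Waning lowers the later visits: if R = 10 and values fall 4-fold by one year after dose 3, the mean is 10/4 = 2.5×LLOQ and P for ELISA is 50%.

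**Step 3: whether the fold increase fills the gap**

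A geometric mean fold of 10 arises if every subject rises 10-fold. It also arises if 20% do not rise and 80% rise 17.8-fold, since 17.8^0.8 = 10. The mean cannot tell these apart. Nor can the responder rate as written, if the non-risers' antibody persists above the cut-off. The reverse cumulative plots in SAP 6.2.1.3 pair each post-dose 3 visit with Baseline, not Pre-dose 3. Dot plots and listings carry no rate or interval.

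**The case against.** The strongest reply is that the definition is a coherent, regimen-level one applied uniformly. It works the same way after the boost, where a subject who responded to the prime alone also counts, and the SAP never calls the post-dose 3 figure a dose 3 responder rate. That stands, and it is the reason to keep the existing rate under a clear label.

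Second, the rise after dose 3 is already analysed. If dose 3 did nothing, the geometric mean fold increase from Pre-dose 3 would be near 1. Table 1 also has its own Pre-dose 3 visit, so the responder rate just before dose 3 should be tabulated on the same definition and the persisting share would be visible. This stands at group level. However, the difference between the rates before and after dose 3 reflects only net movement across the cut-off. If nearly all subjects already qualify before dose 3, the two rates are close whether all subjects rise or almost none do.

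Third, the stakes are limited. Post-dose 3 ELISA is an exploratory objective, the substudy's secondary objective is safety and tolerability, and no hypothesis is tested. This stands in full. For ELISpot and ICS the point is weaker still: substudy PBMC samples are optional, SAP 6.1 lists no collection after dose 3 (in a list that is not exhaustive), and median fold increases from Pre-dose 3 come with quartiles.

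**Conclusion.** The point holds in a limited form. At every post-dose 3 visit the responder comparator is the pre-prime sample, and no planned summary gives the proportion of subjects who respond to dose 3. ELISA and VNA are the main concern.

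A reader might infer more: that every subject without a rise is counted at every post-dose 3 visit, or that the rate will sit near 100% whatever dose 3 does. The documents do not support this. A non-riser counts only while the value stays above the cut-off (2.5×LLOQ for ELISA and 2×LLOQ for VNA if baseline was negative, or the same multiple over a positive baseline). Waned subjects, some with high pre-prime values, and antibody-negative placebo recipients are not counted. The Phase 1 statement describes stability without giving a level relative to the LLOQ.

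The affected share therefore cannot be fixed. Under the assumed R of 1 to 50 and SD of 0.3 to 0.5, it runs from about 9% to 100% of baseline-negative non-risers for ELISA at a single visit. A large share among active recipients is plausible if the Phase 1 stability carries over, but that remains an assumption. The consequence is a descriptive, exploratory rate that is open to misreading.

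**What to change.** For post-dose 3 ELISA and VNA time points, add a second responder flag whose comparator is the Pre-dose 3 value, taken from the Pre-dose 3 visit already in SAP Table 1. Keep the same multiples: more than 2.5-fold for ELISA and more than 2-fold for VNA if Pre-dose 3 is positive, and above 2.5×LLOQ or 2×LLOQ with a positive sample if it is negative. Do the same for ELISpot (2×threshold) and ICS (2×LLOQ) where substudy PBMC samples exist. Report the new rate with its Clopper-Pearson interval. Keep the existing rate and label it as cumulative versus pre-prime.

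The cost is SAP wording, one derived variable and one table. The pre-dose 3 serum is already scheduled in the protocol's Cohort 1 substudy schedule and needed for the fold increases. The dose 3 responder rate may be lower than the cumulative rate. It need not be much lower: if a rise of at least 10-fold is seen again, most active subjects would pass 2.5-fold under either comparator.

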6.2.1.2. Data Handling Rules

For ELISA binding antibody responses, values below the LLOQ will be imputed with LLOQ/2. For the calculation of fold increases, the values below LLOQ will be imputed with the LLOQ.

For VNA titers, values below the assay-specific LLOQ or less than $3 \times$ aMLV will be imputed with half of the assay-specific LLOQ. For the calculation of fold increases, values that are below the assay-specific LLOQ or less than $3 \times$ aMLV will be imputed with the assay-specific LLOQ.

Remark: If an aMLV titer (negative control) is a censored value (ie, <40), then it will be imputed with 40 before proceeding with further computations.

6.2.1.3. Analysis Methods

The humoral immune responses (ELISA [units/mL] and VNA [IC_{50} titer]) will be evaluated separately for each cohort. Within each cohort, the data will be presented by vaccination schedule. See Section 2.4 (and Table 4) for details on the subgroup analyses that will be performed.

Except for VNA analysis of the HIV-infected subjects (Cohort 2a), the humoral immune responses of all other cohorts will be analyzed as follows. Summary statistics (ie, geometric means and corresponding 95% CIs) will be calculated and presented for ELISA (units/mL) binding antibody responses and VNA (IC_{50} titers) at each time point. The geometric mean fold increase (from Pre-dose 1, Pre-dose 2 and Pre-dose 3 [only for the Cohort 1 substudy]) with corresponding 95% CI will also be presented per time point for these parameters.

Regimen profiles of the geometric mean concentrations with 95% CIs will be presented. Additional regimen profiles of the geometric mean concentrations with 95% CIs will be generated by pre-existing antibody response against Ad26 vector (ie, pre-existing Ad26 versus no pre-existing Ad26). In addition, graphs of the reverse cumulative distributions (ie, percentage of subjects versus the magnitude of the antibody response levels) will be provided for the following time points, if available:

- Baseline and Pre-dose 2
- Baseline and Day 21 Post-dose 2
- Baseline and 180 days Post-dose 2
- Baseline and Day 365 Post-dose 1
- Baseline and 4 days Post-dose 3
- Baseline and 7 days Post-dose 3
- Baseline and 21 days Post-dose 3
- Baseline and Day 180 Post-dose 3
- Baseline and Day 365 Post-dose 3

For both ELISA (ELISA units/mL) and VNA (IC₅₀ titer), additional graphical representations (on a log₁₀-scale) will be provided using dot plots (with distinction between positive and negative sample interpretations), by vaccination schedule.

Responder rates and positive sample interpretation will be summarized (ie, showing number, percentage and the exact 95% Clopper-Pearson CI) for ELISA (ELISA units/mL) antibody responses and VNA (IC₅₀ titers) per time point. A data listing will also be generated.

For the HIV-infected subjects (Cohort 2a), only positive sample interpretation will be summarized (ie, showing number, percentage and the exact 95% Clopper-Pearson CI) per time point.

6.2.2. Cellular Immune Responses

6.2.2.1. Parameters

Cellular immune responses, as measured by the following assays, will be analyzed:

- **ELISpot:** EBOV GP-specific IFN- γ producing T cells, measured as the number of spot-forming units per million peripheral blood mononuclear cells (SFU/10⁶ PBMC).

The following will be defined for ELISpot:

- **Sample interpretation:** Sample positivity (interpretation) will be determined for each of the peptide pools separately. If a sample is considered positive for at least one of the peptide pools, the sample is considered positive. A sample will be considered positive when the EBOV peptide pool-stimulated readout is greater than 3-fold the mock (unstimulated) readout and the mock-subtracted value is greater than the threshold. The threshold is assay-specific and will be provided by the vendor.
- **Responder:**

- If sample interpretation is negative at baseline but positive post-baseline and the post-baseline value is greater than $2 \times$ Threshold; OR
- If sample interpretation is positive at both baseline and post-baseline and there is a greater than 2-fold increase from baseline.

- **ICS:** The following responses will be measured:
 - CD4+: IL-2, IFN- γ , and/or TNF- α responses to EBOV GP.
 - CD8+: IL-2, IFN- γ and/or TNF- α responses to EBOV GP.

For each type of cytokine expressing T cell (CD4+ or CD8+), each peptide pool (GP1 or GP2) and both negative controls, the database contains the total cell count of cytokine expressing T cells and the marginal cytokine expressing T cells subsets (in the text below referred to as “*cytnum*”) and the total number of cells (*nsub*). For the computation of the background adjusted percentage for any peptide pool (GP1 and GP2 combined) for the total cytokine response and the “pure” cytokine combinations, see the detailed steps outlined in Attachment 6.

In addition, the following will be defined for the ICS:

- **Sample interpretation:** For each antigen, the total cytokine count of the considered antigen is compared with the total cytokine count in all negative control samples with the Fisher’s exact test (Table 5). The test is repeated for both peptide pools (GP1 and GP2) and for each antigen. If the observed p-value for at least 1 peptide pool (GP1 or GP2) is below $10^{-5}/2$ (division by 2 due to Bonferroni correction as this is done for each pool), the sample interpretation is considered positive for that antigen².

Table 5: Generic Contingency Table for the Fisher’s Exact Test

	GP _x ($x = 1$ or 2)	Negative controls
Cells expressing cytokines	$cytnum_x$	$cytnum_neg1 + cytnum_neg2$ (or in case of 1 negative control: $cytnum_neg$)
Cells not expressing cytokines	$nsub_x - cytnum_x$	$(nsub_neg1 + nsub_neg2) - (cytnum_neg1 + cytnum_neg2)$ (or in case of 1 negative control: $nsub_neg - cytnum_neg$)

cytnum: marginal cytokine counts; *cytnum neg1*: cell counts of one negative control; *cytnum neg2*: cell counts for the other negative control; *nsub*: total number of cells for the cytokine assay; *nsub neg1*: total number of cells for one control assay; *cytnum neg2*: total number of cells for the other control assay. Note that a given negative control (ie, in case of 2 negative controls) cannot be linked to a specific peptide pool (GP1 nor GP2) because the necessary linking information will not be available in the database.

- **Responder:**
 - If sample interpretation is negative at baseline but positive post-baseline and the post-baseline value is greater than $2 \times$ LLOQ; OR
 - If sample interpretation is positive at both baseline and post-baseline and there is a greater than 2-fold increase from baseline in background adjusted total cytokine response.

